9.5.1. Emergency Unblinding

In case of an emergency, the investigator has the sole responsibility for determining if unblinding of a patient's treatment assignment is warranted. Patient safety must always be the first consideration in making such a determination. If the investigator decides that unblinding is warranted, the investigator should make every effort to contact the Lilly CRP prior to unblinding a patient's treatment assignment unless this could delay emergency treatment of the patient. If a patient's treatment assignment is unblinded, Lilly must be notified immediately.

9.5.2. Inadvertent Unblinding

Every effort will be made to blind both the patient and the investigator to the identity of the treatment, but the inadvertent unblinding of a patient may occur. A double-blind study design is known to be imperfect in the oncolytic setting because the potential for individual unblinding exists due to treatment-related signs and symptoms. If an investigator, site personnel performing assessments, or patient is unblinded, the unblinding will not be sufficient cause (in and of itself)

for that patient to be discontinued from study therapy or excluded from any safety or efficacy analyses.

Additionally, there may be ethical reasons to have the patient remain on the study treatment. For patients to continue on study treatment in the event of unblinding, the investigator must obtain specific approval from a Lilly CRP for the patient to continue in the study.

9.6. Concomitant Therapy

Appropriate documentation of all forms of premedications, supportive care, and concomitant medications must be captured at each visit in the CRF. Concomitant medications and supportive care therapies must also be documented at the time of discontinuation and at the 30-day short-term follow-up visit.

No other chemotherapy, other anticancer therapy, immunotherapy, hormonal cancer therapy (except therapy of hormone-sensitive prostate cancer patients who are stable on GnRH agonist therapy and breast cancer patients who are stable on antiestrogen therapy [eg, an aromatase inhibitor]), radiation, surgery for cancer, or experimental medications, including herbal supplements intended to treat the cancer, will be permitted while patients are on study treatment. The need for any form of radiotherapy (including palliative) will be cause for early discontinuation from the study. In addition, any disease relapse requiring other forms of specific antitumor therapy will also necessitate early discontinuation from the study.

Prophylactic intrathecal therapy is allowed for patients with high risk of CNS disease as long as spinal fluid is negative for blasts and no other evidence of active CNS disease.

Patients should receive full supportive care, if necessary. Supportive care is given with the intent to maximize quality of life. Those therapies considered acceptable include, but are not limited to control of infections, treatment of TLS, management of asparaginase toxicity, management of steroid side effects, use of transfusions, use of granulocyte colony-stimulating factor (G-CSF), use of antiemetics, nutritional support, and treatment of pain. Patients will receive supportive care as judged by their treating physician. If it is unclear whether a therapy should be regarded as supportive care, the investigator should consult the Lilly CRP. The use of any supportive care therapy should be reported on the CRFs.

The protocol does not permit the routine use of colony-stimulating factors or erythropoiesis-stimulating agents (ESAs) during treatment. The protocol does not allow the use of products that stimulate thrombopoiesis. Erythropoietic therapy may be considered for treatment of chemotherapy-induced anemia for patients with hemoglobin <10 g/dL after the patients has been counseled about the risks and benefits of ESA use (Smith et al. 2006; Rizzo et al. 2008).

Because recommendations on the use of ESAs are rapidly evolving, investigators should frequently refer to the National Comprehensive Cancer Network (NCCN), American Society of Clinical Oncology, American Society of Hematology, and/or Centers for Medicare and Medicaid Services websites for the latest guidelines or follow local guidelines.

In the event of diarrhea, the following supportive measures are allowed: hydration, octreotide, and antidiarrheals, including opioids.

If diarrhea is severe (requiring intravenous rehydration) and/or associated with fever or severe (Grade 3 or 4) neutropenia, broad-spectrum antibiotics must be prescribed taking into account the local prevalence of infection agents and their probable resistance. Patients with severe diarrhea or any diarrhea associated with severe nausea and vomiting **should be hospitalized** for supportive care including antiemetics, intravenous hydration and correction of electrolyte imbalances. Events that require a patient to be hospitalized are considered SAEs (see Section 10.3.1.1).

Patients experiencing febrile neutropenia, especially with diarrhea or dyspnea, should be managed in a hospital setting according to standard procedures, with the urgent initiation of intravenous antibiotic therapy.

The use of allopurinol should be considered as an adjunct to appropriate use of hydration in prophylaxis of TLS. Evaluation of hydration status and changes in kidney function, serum electrolytes, and uric acid levels may assist in both prophylaxis for and management of acute renal function changes and TLS. When there is concern about the level of disease burden and effects of potential rapid cytoreduction, or if the patient has high baseline uric acid levels, prophylaxis for TLS with allopurinol or another therapeutic substitute may be considered. When used for prophylaxis, allopurinol should be administered orally once daily starting at a minimum the day before the first study drug dose. Allopurinol may be discontinued or dose adjusted during study treatment at the investigator's discretion, for example, based on renal function. If allopurinol is contraindicated, investigators may consider the use of an appropriate therapeutic substitute.

9.7. Treatment Compliance

Patient compliance with study medication will be assessed at each visit. Compliance will be assessed by direct questioning, counting returned capsules. Furthermore, the patient or caregiver will have to complete a diary for Cycles 1 and 2 at time points related to the PK sample schedule as described in [Attachment 3](#). In addition, any Day 1 dosing date in Cycles >2 have to be documented.

The patient must take $\geq 75\%$ of the intended doses to be deemed compliant with study drug administration. Similarly, a patient will be considered significantly noncompliant if he or she is judged by the investigator to have intentionally or repeatedly taken more than the prescribed amount of medication. Any missed doses during a cycle will be omitted and not replaced. In the event of a missed dose, a patient should resume and continue dosing, beginning with the next scheduled dose.

Potential discontinuation of a patient due to study drug noncompliance will be discussed between the investigator and the Lilly CRP before the final determination is made to discontinue the patient. If a patient is discontinued due to study drug noncompliance, the patient may be replaced.

9.7.1. Evaluable Patients Phase 1 Parts A and B

Patients who withdraw from the study before receiving study drug(s) will be replaced and will not be included in the safety or efficacy assessments. Safety analyses will be conducted on all patients who have received at least 1 dose of any study drug, regardless of whether they are deemed evaluable for the assessment of a dose level.

Patients who are not evaluable for PK, but who complete 1 cycle of therapy, may be replaced upon consultation with the investigator(s) and the Lilly CRP to ensure adequate PK data, unless accrual to that cohort has stopped due to a DLT. Patients who are evaluable for PK are defined as patients who have a sufficient number of PK samples to evaluate PK parameters after at least 1 dose of LY3039478.

Patients who are discontinued from the study before completing Cycle 1 will be deemed nonevaluable for assessment of a dose level, unless they experience a DLT prior to withdrawal.

If patients are noncompliant during Cycle 1 due to reasons other than drug-related toxicity, they will be considered nonevaluable.

Nonevaluable patients will be replaced to ensure that 3 patients complete 1 cycle of therapy at each dose level, unless accrual to that cohort has stopped due to a DLT.

9.7.2. Evaluable Patients Phase 2

In the Phase 2 portion of the study, patients will be considered evaluable after randomization as per definition of the intent-to-treat analysis set (Section 12.2.1).

10. Efficacy, Health Outcome/Quality of Life Measures, Safety Evaluations, Sample Collection and Testing, and Appropriateness of Measurements

Written informed consent must be obtained prior to any study-specific pretreatment evaluations.

Study procedures related to efficacy, safety, health outcome/quality of life measures, sample collection and testing assessments and their timing are described in the sections below and shown in the Study Schedule ([Attachment 1](#)).

10.1. Efficacy Measures

10.1.1. Study Assessments

10.1.1.1. Pretreatment (Baseline)

For T-ALL patients, a bone marrow biopsy and/or aspirate will be obtained to locally assess bone marrow cellularity and to determine the percentage of leukemic blasts within 2 weeks and no less than 1 day before the first dose of study drugs. The results of this bone marrow biopsy and/or aspirate will serve as the baseline assessment for efficacy; therefore, the results will not be required to be received before study drug administration. In addition, a computed tomography (CT) or magnetic resonance imaging (MRI) of the thorax and abdomen (including the pelvis) will be performed within 4 weeks and no less than 1 day before the first dose of study drug.

For T-LBL patients, baseline tumor measurements will be performed within 4 weeks and no less than 1 day before the first dose of study drugs. Positron emission tomography-computed tomography (PET-CT) is the preferred method of measurement for FDG-avid lymphomas. A CT, including spiral CT, or MRI of the thorax and abdomen is indicated for non-avid histologies.

For all patients with suspected CNS involvement, a lumbar puncture will be performed within 14 days before the first dose of study drugs. For patients with neurological signs or symptoms at diagnosis, a CT/MRI of the brain and/or affected spinal cord is required within 4 weeks before the first dose of study drugs.

For patients continuing treatment after study completion, efficacy assessments (frequency and type of assessments) will be at the discretion of the investigator and based on the standard of care.

10.1.1.2. During Study Treatment

For T-ALL patients, during the treatment phase of the study, blood samples will be obtained to monitor disease burden weekly according to the Study Schedule ([Attachment 1](#)) during Cycle 1 and biweekly thereafter. Additionally, a bone marrow core biopsy and/or aspirate sample will be obtained on Day 28 (-3 days) of Cycle 1. If the morphologic result does not provide a clear response and it is clinically indicated by the investigator, a second bone marrow examination should be repeated 1 week later. For T-ALL and where clinically indicated, the CT/MRI will be repeated on Day 28 (-3 days) of Cycle 1. A response (CR or PR) must be confirmed no less than

28 days from the first evidence of response by bone marrow core biopsy and CT/MRI as indicated. If 2 consecutive bone marrow assessments demonstrate no tumor with adequate cellularity, bone marrow assessments will be discontinued unless there is evidence of relapse. In case of CR by CT/MRI on 2 assessments no less than 28 days apart the interval between assessments may be increased to every 2 months.

In T-LBL patients, the method of assessment used at baseline must be used consistently for tumor assessment and will be repeated every other cycle starting on Day 28 (-3 days) of Cycle 2. For T-LBL patients followed by CT/MRI, response (CR or PR) must be confirmed no less than 28 days from the first evidence of response. Thereafter, a responding patient will be followed every other cycle until objective progression is observed.

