8.1. Summary of Study Design

Study JJCB is a multicenter study consisting of a nonrandomized, open-label, dose-escalation Phase 1 study followed by a randomized, double-blind, Phase 2 study in patients with relapsed or refractory T-ALL/T-LBL. The Phase 1 portion of the study will consist of 2 different patient populations, an adult (Part A) and a pediatric (Part B), and will define the recommended dose of LY3039478 in combination with dexamethasone in each of these populations. The randomized Phase 2 study will be a double-blinded, multicenter evaluation to determine if the CR and CRI (CR with incomplete blood count recovery) rate in adult patients with relapsed/refractory T-ALL/T-LBL treated with LY3039478 in combination with dexamethasone exceeds that of those patients treated with placebo in combination with dexamethasone. [Figure JJCB.8.1](#) illustrates the study design.

Eligible adult patients will receive LY3039478 administered orally TIW and dexamethasone administered 24 mg orally Days 1 to 5 every other week. In Part B (pediatric patients), dexamethasone is administered at 10 mg/m² BID, orally, Days 1 through 5 every other week. A cycle is defined as 28 days of treatment (4 weeks).

The Phase 1 portion will start with the adult cohort (Part A). The decision to proceed with the pediatric dose exploration (Part B) will be made after safety analysis of the adult cohort.

The dose escalation, described in Section [9.2.1](#), will be guided primarily by safety assessments from Days 1 through 28 of Cycle 1 for patients in all cohorts. Dose escalation will occur until the MTD (defined in Section [9.2.2](#)) is determined. Patients will be enrolled in Part A with the first dose level of 50 mg LY3039478, TIW. [Table JJCB.9.2](#) outlines the proposed dose-escalation scheme. Dose levels will be determined based on the review of the safety, PK, and PD data from the previous doses. Additional dose levels (to a maximum of 200 mg TIW) may be explored if necessary. No dose escalation will occur beyond MTD. In Parts A and B, the sample size is estimated to be approximately 13 to 16 patients in each part depending on the relationship between exposure and toxicity as well as the relationship between exposure and pharmacological effects.

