The patient, caregiver, or clinic personnel will record time and amount of each dose in the patient diary on days of PK assessment ([Attachment 3](#)) during Cycle 1 and Cycle 2, and study monitors will cross-reference clinic records at the site to verify accuracy. For cycles 3 and beyond first and last dose date and amount of both drugs for each individual cycle will be documented. Clinic personnel will instruct patients to pay particularly close attention to record this information accurately.

For Cycle 2 and beyond, a delay of ≤ 7 days in the start of a cycle (Dose 1) for justifiable reasons (for example, inclement weather, holidays, or weekends) other than toxicity will be permitted and does not constitute a protocol violation.

For Cycle 2 and beyond, a delay of ≤ 21 days in the start of a cycle (Dose 1) to allow for recovery from toxicity will be permitted and does not constitute a protocol violation (refer to Section 9.4.2).

The investigator or his/her designee is responsible for the following:

- explaining the correct use of the drugs and planned duration of each individual's treatment to the patient/site personnel/legal representative
- verifying that instructions are followed properly
- maintaining accurate records of study drug dispensing and collection
- returning all unused medication to Lilly or its designee at the end of the study

In some cases, sites may destroy the material if, during the investigator site selection, the evaluator has verified and documented that the site has appropriate facilities and written procedures to dispose clinical trial materials.

Patients will be instructed to contact the investigator as soon as possible if they have a complaint or problem with the study drug so that the situation can be assessed.

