9.4.2. Dose Adjustments for LY3039478 between Cycles

Before the start of each cycle, nonhematological toxicities (except alopecia and fatigue) must resolve to baseline. The start of LY3039478 may be delayed up to 21 days to allow sufficient time for recovery. Patients experiencing non-transient Grade 4 nonhematological toxicity or not recovering from toxicity within 21 days should be discontinued from the study.

The dose of LY3039478 should be reduced to the dose level administered in the previous cohort for all subsequent cycles of therapy if the investigator determines that it is in the best interest of the patient or if the patient experienced at least 1 of the following events:

- DLT (in Cycle 1 for patients in Phase 1)
- DLET (in Cycle 2 or beyond for patients in Phase 1, or in any cycle for patients in Phase 2)
- omission of more than 7 doses of LY3039478 in a single cycle for tolerability

For patients requiring a dose reduction, re-escalation to the original dose level is not permitted.

A second dose reduction is allowed only for patients treated at adult dose level ≥ 75 mg or pediatric equivalent (dose may be reduced to 25 mg or pediatric equivalent). Dose reduction by more than 2 dose levels is not permitted; patients requiring dose reduction by more than 2 dose levels should be discontinued from the study.

If a patient experiences a DLET at the second reduced dose level, then the patient will be discontinued from the study. If a patient requires omission of more than 3 doses for tolerability at the reduced dose levels, then treatment may continue if the investigator determines that the patient is receiving clinical benefit.

In the Phase 2 portion of the study, investigators will treat all patients as if the patient is receiving active study drug, LY3039478, and will adjust doses accordingly.

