10.1.1.3. Posttreatment Discontinuation Follow-Up

Postdiscontinuation follow-up during the study period will be conducted as described in the Study Schedule ([Attachment 1](#)).

For T-ALL patients who are in remission, blood samples should be obtained every 1-3 months. After relapse, no blood sample analysis is required. The patient will be followed approximately every 90 days (\pm 14 days) until the patient's death or overall study completion. Bone marrow assessment will be performed at time of treatment discontinuation or in the 30 Day follow-up period only if not assessed in the prior 8 weeks.

For T-LBL patients who discontinue study treatment without objectively measured progressive disease, the investigative sites will continue to monitor patients and periodically evaluate tumor response approximately every 8 weeks by the same method used at baseline and throughout the study until the patient has objective disease progression, or until the final analysis of OS is performed. After the patient has objective disease progression, radiologic tests are no longer required and the patient will be followed approximately every 90 days (\pm 14 days) until the patient's death or overall study completion.

Response (CR or PR) should be confirmed before the initiation of additional anticancer therapy. However, initiation of new therapy should not be delayed solely to confirm response.

After the primary/final analysis of OS, efficacy assessments (frequency and type of assessments) will be at the discretion of the investigator, based on the standard of care.

Lilly will continue to collect survival data on all patients but may reduce data collection for other efficacy data. Lilly will notify investigators when this reduced data collection can begin.

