#### **Time to Event Endpoints**

For the secondary efficacy endpoints OS, RFS, and EFS, the Kaplan-Meier method (Kaplan and Meier 1958) will be used to estimate the survival curves as well as survival rates at various

prespecified time points (12 months for OS, 6 and 12 months for RFS and EFS) for each treatment arm.

The secondary efficacy endpoint DoR is subject to competing risk of death without relapse; therefore, the cumulative incidence of relapse (Gray 1988; Pepe and Mori 1993; Gooley et al. 2001) will be used. In the calculation, patients who did not have the event will be considered right-censored observations.

The comparison of the survival curves between treatment groups will be conducted by a log-rank test. Exploratory analyses for the comparison of the survival curves between treatment groups may additionally be conducted by a stratified log-rank test with some of the following stratification variables: initial diagnosis (T-ALL phenotype, T-LBL), response to last therapy (refractory or relapsed), age, number of prior therapies ( $\leq 2$ ,  $> 2$ ), NOTCH-1/FBXW7/RAS/PTEN status.

The Cox proportional hazard model (Cox 1972) with treatment as a factor will be used to estimate the hazard ratio and corresponding 95% CI with Wald's test p-value after adjusting for the following potential predictive/prognostic variables: initial diagnosis (T-ALL phenotype, T-LBL), response to last therapy (refractory or relapsed), age, number of prior therapies ( $\leq 2$ ,  $> 2$ ), NOTCH-1/FBXW7/RAS/PTEN status.

The unadjusted impact of patient baseline disease characteristics listed in Section 6.8 on OS and EFS will be explored using Cox proportional hazard models (Cox 1972) with the baseline characteristic as a factor (continuous variables split at median) and the hazard ratio and corresponding 95% CI plotted on a forest plot. Any characteristics found to be significant prognostic markers for EFS or OR may be included as additional covariates in COX proportional hazard model analyses to compare treatment arms.

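### On-treatment T-LBL scans follow cycle days that toxicity can postpone; if delays are more frequent on LY3039478, the EFS comparison is tilted slightly towards that arm

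*Protocol*

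**What the plan says.** **Scan timing on treatment.** Protocol Section 10.1.1.2 says that tumor assessment in T-LBL "will be repeated every other cycle starting on Day 28 (-3 days) of Cycle 2". Section 10.1.2 puts the first response assessment on the same cycle day, but with a window of ±3 days. The Phase 2 schedule in Attachment 1 shows T-LBL imaging in Week 4 under a Cycle 2-n heading, without restricting it to alternate cycles.

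**Permitted delay.** A cycle lasts 28 days (Section 8.1). For Cycle 2 and beyond, Section 9.2 says that "a delay of ≤ 21 days in the start of a cycle (Dose 1) to allow for recovery from toxicity will be permitted". Section 9.4.2 repeats the limit: "The start of LY3039478 may be delayed up to 21 days to allow sufficient time for recovery". Patients "not recovering from toxicity within 21 days should be discontinued from the study". SAP Table JJCB.6.1 counts cycle day from the actual first dose in the cycle, so a late start moves Day 28, and the scan, with it.

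**Scan timing off treatment.** Section 10.1.1.3 uses the calendar: for T-LBL patients who stop without progression, sites "periodically evaluate tumor response approximately every 8 weeks by the same method used at baseline".

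**Use in the analysis.** SAP Section 6.11 dates progression at the assessment that shows it, and EFS counts treatment failure, relapse from CR and death. For EFS, "The comparison of the survival curves between treatment groups will be conducted by a log-rank test", with an adjusted Cox model and Kaplan-Meier rates at 6 and 12 months. The sensitivity analyses in Table JJCB.6.2 deal with transplant, missed assessments, inadequate baseline and loss to follow-up. None deals with assessments that are late or unequally timed between arms.

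**The concern.** Progression found by imaging is recorded at the next scan, so its recorded date depends on when scans are done. If one arm is scanned on a later calendar than the other, equal true progression times give unequal recorded ones. Here the schedule moves with toxicity, which may itself depend on treatment, and no text holds scans in place during a dosing delay.

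What is at stake is a secondary endpoint: EFS in T-LBL, and the pooled EFS comparison in proportion to the T-LBL share. Scan dates cannot be repaired at analysis, so the remedy has to be in the protocol.

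**Working it through.** The plan gives no power, event count or effect size for EFS, so there is no figure of its own to reproduce. Its stated 82% power concerns ORR and plays no part here.

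**1. Scan dates.** Inputs: 28-day cycles (8.1), a scan on Day 28 of every second cycle (10.1.1.2), and a delay d of 0 to 21 days at each start from Cycle 2 (9.2, 9.4.2). Scan k falls at the end of Cycle 2k, after 2k − 1 starts that can be delayed:

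day of scan k = 56k + d(2k − 1)

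- d = 0: Days 56, 112, 168
- d = 7: Days 63, 133, 203
- d = 21: 56 + 21 = 77; 112 + 63 = 175; 168 + 105 = 273

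The gap between scans is 56 + 2d, at most 56 + 42 = 98 days. The average lag from progression to scan is about half the gap: 28 days, rising to 49. If Attachment 1 means a scan in every cycle, the gap is 28 + d, at most 49 days.

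**2. Mean recorded time.** Assumptions: equal true hazards, true median progression 42 to 120 days, and delays in one arm only. Mean recorded time to progression in T-LBL lengthens by 5.5 to 6.1 days if 25% of starts slip 21 days, by 10.4 to 11.2 days if 50% do, and by 18.6 to 19.7 days if all do.

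**3. Medians and the 6-month rate.** These need not move the same way as the mean. With d = 21, progression on Days 57 to 77 is dated Day 77 instead of Day 112, which is earlier. With a true median of 60 days the recorded median falls from 112 to 77 days; with 90 days it rises from 112 to 175. Ignoring deaths, recorded 6-month EFS is 2^(−s/m), where s is the last scan before 6 months and m the true median:

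- m = 60: 2^(−168/60) = 14.4% with no delay; 2^(−133/60) = 21.5% with d = 7; 2^(−175/60) = 13.2% with d = 21
- m = 84: 2^(−168/84) = 25.0% with no delay; 2^(−175/84) = 23.6% with d = 21

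**4. Log-rank comparison with no true effect.** Assumptions: 40 v 20 patients, median progression 60 days, median death 180 days, 21-day delays on LY3039478 only, and T-ALL progression dated exactly. There were 6000 runs per row. False positives are one-sided in favour of LY3039478, nominal 2.5%.

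| T-LBL share | Starts delayed | Median HR | False positives |
|---|---|---|---|
| 15% | none | 0.99 | 3.4% |
| 15% | 25% | 0.99 | 3.2% |
| 15% | all | 0.97 | 4.2% |
| 30% | none | 0.99 | 3.0% |
| 30% | 25% | 0.98 | 3.4% |
| 30% | all | 0.93 | 5.7% |
| 100% | none | 0.99 | 2.8% |
| 100% | 25% | 0.96 | 5.2% |
| 100% | all | 0.73 | 30.2% |

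The standard error of a 3% rate is √(0.03 × 0.97 / 6000) = 0.2 percentage points, so at 15% to 30% T-LBL with 25% of starts delayed no change in error rate can be distinguished.

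A second simulation used 4000 trials per scenario and modelled progression only. Its medians were 8 or 12 weeks, with 30% to 50% of LY3039478 cycles and 0% to 10% of placebo cycles delayed by 7 to 21 days. Relative to no delay, the hazard ratio was 0.89 to 0.97 if all patients have T-LBL and 0.96 to 0.99 if half do. At 30% T-LBL the shift was within simulation error.

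**The case against.** **Unequal delays are not documented.** A reader might infer that T-LBL EFS is in fact lengthened in favour of LY3039478. The documents do not support that, because they give no delay rate for either arm. Section 5.1.6 reports single-agent adverse events (vomiting 41.0%, diarrhea 30.8%), not delays. Dexamethasone is given in both arms and is expected to lessen gastrointestinal toxicity (5.2), and investigators adjust doses as if every patient were on active drug (9.4.2). This stands, and the point is therefore conditional. A difference remains plausible: nonhematological toxicity other than alopecia and fatigue has to return to baseline before each cycle, and nothing says that dexamethasone removes the difference.

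**The direction is not fixed for every summary.** A reader might also infer that the more toxic arm always gains. Step 3 shows otherwise; only the mean and, on average, the hazard comparison have one direction.

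**The large error rates describe no planned test.** The rows with 100% T-LBL are a 60-patient trial without T-ALL. EFS is tested on both diseases together, and T-LBL alone appears only in exploratory subgroup work. The documents give no T-LBL share.

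**Several features limit the effect.** Deaths and progression found between scheduled scans do not depend on the schedule. A patient who does not recover within 21 days stops treatment and moves to calendar scans. Day 175 needs three successive maximum delays. The 98-day gap rests on the every-other-cycle text, which Attachment 1 does not repeat.

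**The primary endpoint.** It is tempting to extend the point to ORR. No such effect is shown: best response uses all assessments up to progression or new therapy, and patients without CR or CRi count as nonresponders.

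**Conclusion.** The mechanism is in the text, and no planned sensitivity analysis covers it. If toxicity delays are more frequent on LY3039478, recorded T-LBL progression is later on average in that arm and the log-rank and Cox comparisons of EFS lean towards it.

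The size is small for the pooled analysis that is planned. Under the assumed partial delay rates the null hazard ratio is about 0.96 to 0.99, depending on the T-LBL share. Even if every LY3039478 cycle start slipped the full 21 days, it would be 0.97 at 15% T-LBL and 0.93 at 30%. Delay rates, T-LBL share, and progression and death times are all assumptions. This is a worthwhile low-cost improvement to a secondary endpoint, not a threat to the primary conclusion.

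**What to change.** In Protocol Sections 10.1.1.2 and 10.1.2 and in Attachment 1, schedule on-treatment T-LBL imaging every 8 weeks by calendar, irrespective of cycle delays or omitted doses, from one fixed anchor and with one stated window. Anchoring at first dose keeps the nominal Days 56, 112 and 168; anchoring at randomization is also workable but shifts the dates by the interval from randomization to first dose. This matches the 8-week rule already used after discontinuation in 10.1.1.3, and it puts both arms on one scan grid, so that the shift due to scan timing is zero.

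In the same edit, reconcile the every-other-cycle text with the Cycle 2-n heading in Attachment 1, and the −3 day window with the ±3 day window. The 8-week follow-up interval in 10.1.1.3 should also be reconciled with the 2 to 4 months in the Attachment 1 follow-up table. No change is needed for the T-ALL CT/MRI that 10.1.1.2 sets on Day 28 of Cycle 1, because it comes before any permitted cycle-start delay.

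The cost is protocol wording: no scans are added to the nominal every-other-cycle schedule, and the dosing and delay rules are untouched. The downside is that in a delayed patient a scan may fall mid-cycle or during a hold, and the first response scan may follow less than two full cycles of treatment. Later scans still count towards best response.
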